2. MEASURES OF DURATION

- Time to Progression: measured from the date of first study treatment to the first date when progressive disease is documented.
 - a. Progressive Disease (PD)-Free Interval (Duration Of Response): measured, in a responder, from the date when a CR, CCR or PR is first noted to the first date at which progressive disease is observed. An ongoing PD-free interval occurs when there is a responder for whom progressive disease has not been noted.

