Second, although ESHAP is very active in low-grade NHL, it is not often utilized by community oncologists as a salvage regimen. Therefore, most pretreated patients have not seen these agents and therefore their lymphomas should be responsive to ESHAP. After treatment with two cycles of preparative ESHAP most patients should have minimal residual disease and therefore have higher response to Zevalin. It is our hypothesis that tumor mass reduction with standard chemotherapy in relapsed follicular lymphoma will result in a significant prolongation of time to progression following Zevalin therapy, changing the natural history of relapsed disease.

The TTP and OS results of this study will be compared with reported outcomes in published trials of Zevalin alone to assess whether there is sufficient improvement to merit further study of this approach in this setting. We have designed the trial to detect an increase in 1-year PFS from a historical value of 50% to 67.3%, which corresponds to an increase in median TTP from 12 months to 21 months.

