7 TREATMENT PLAN

All patients who qualify for this study will receive chemotherapy with ESHAP followed by treatment with Zevalin

7.A ESHAP REGIMEN DOSING

ESHAP chemotherapy: Patients will receive 2 cycles of cytoreductive chemotherapy according to the schedule described below. (Table 7)

TABLE 7 ESHAP CHEMOTHERAPY PLUS ZEVALIN

DRUG	DOSE	ROUTE	DAYS	INTERVAL
Etoposide	$40 \text{ mg/m}^{2/} \text{day}$	IV infusion over 1 hour	1,2,3,4	q 28 days for 2 cycles
Methylprednisolone	250 mg/day	IV push	1,2,3,4	q 28 days for 2 cycles
		_		
Cytarabine	2000 mg/m^2	IV infusion over 2 hours	4	q 28 days for 2 cycles
Cisplatin	25 mg/m ² /day	IV infusion at 1mg/min	1,2,3,4	q 28 days for 2 cycles

- The cycle length will be 28 days if bone marrow recovery allows. If recovery requires an additional week, then the second cycle will be postponed for a week.
- Either pegfilgastrim or filgastrim may be given at the investigator's discretion.

7.B RITUXIMAB, 111 IN ZEVALIN, AND 90 Y ZEVALIN ADMINISTRATION

The rituximab + ibritumomab tiuxetan regimen is given 4-6 weeks after completion of the second cycle of ESHAP. Treatment can be completed within 7 - 9 days in an outpatient setting

TABLE 8
Rituximab, 111In Zevalin, AND 90Y Zevalin Administration

AGENT	DOSE	ROUTE	DAYS	NOTES
Rituximab	250 mg/m ²	Slow IV	1, then 7, 8 or 9	Give prior to 111 In Zevalin
¹¹¹ In Zevalin	5 mCi	Slow IV push over 10 minutes	1	Give within 4 hours after rituximab
⁹⁰ Y Zevalin	Depends on platelet count (see Section 7.B.3)	Slow IV push over 10 minutes	7, 8, or 9	Give within 4 hours after rituximab

7.B.1 Rituxan & 111 In Zevalin Administration

1.6 mg of ¹¹¹In Zevalin (5.0 mCi of ¹¹¹In) will be used for radioimaging. The imaging dose of ¹¹¹In Zevalin will be administered by a 10-minute slow IV push injection immediately following the infusion of Rituxan. ¹¹¹In Zevalin may be directly injected by stopping the flow from the IV bag and injecting the radiolabeled antibody directly into the line. A 0.22 micron filter must be on line between the patient and the infusion port. Flush the line with at least 10 mL of normal saline after ¹¹¹In Zevalin has been injected. (See Appendix H).

a. Oral premedication (2 tablets [325 mg] of acetaminophen and 50 - 100 mg oral diphenhydramine hydrochloride) may be administered 30 - 60 minutes prior to starting each infusion of rituximab.

7.B.2 Radioimaging Schedule

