12 STATISTICAL CONSIDERATIONS

12.A Study Design

This is a two- institution phase II trial to determine the efficacy and safety of the ESHAP-Zevalin combination therapy for the management of relapsed (CD 20+) follicular lymphoma. Patients must have received at least one, but no more than 2 prior treatments for follicular lymphoma.

The primary objective of this phase II clinical trial is to evaluate the 1-year progression-free survival (PFS) of patients with relapsed follicular NHL treated with ESHAP chemotherapy for cytoreduction (2 cycles) followed by Y-90 ibritumomab tiuxetan (Zevalin) radioimmunotherapy, compared to what would be expected historically for patients treated with Zevalin without prior cytoreduction. For this patient population, a 1-year PFS of 67.3% will be considered highly encouraging, compared to an historical rate around 50%. These values correspond to approximate median times to progression of 21 months and 12 months, respectively, assuming exponential survival.

12.B. Sample Size

The planned sample size of 52 evaluable patients is based on testing the null hypothesis that the true 1-year PFS is \leq 50%, versus an alternative hypothesis that the true rate is \geq 67.3% with this therapeutic approach. Based on the number of patients seen at the Arizona Cancer Center with relapsed follicular lymphoma requiring treatment, the anticipated accrual rate is 2 patients per month. It is estimated that accrual to the study would be completed within 26 months. All patients who receive at least one dose of chemotherapy will be considered evaluable and included in the analysis. In the unlikely event that an enrolled patient does not receive treatment, an additional patient will be registered.

12.C Method of Analysis

The following are the design characteristics based on a chi-square test for one binomial population at the one-sided 0.10 significance level. If the true PFS is $\leq 50\%$, then there is a maximum probability of 0.10 of concluding that this treatment approach is sufficiently promising that it should be accepted for further study (false positive rate). Alternatively, if the true PFS is $\geq 67.3\%$, then the maximum probability of

rejecting this treatment approach for further study in this setting is 0.10 (false negative rate), equivalent to a power of 90%.

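### The 1-year test, counted from first ESHAP, judges the whole ESHAP-Zevalin sequence; it cannot by itself show longer time to progression after Zevalin, and no planned analysis does

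*Combined protocol and SAP*

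**What the plan says.** - **Time zero.** Appendix D, Measures of Duration: "Time to Progression: measured from the date of first study treatment to the first date when progressive disease is documented". The first study treatment is ESHAP Cycle 1 Day 1. Table 2 of the same appendix measures PFS from entry onto the trial, which is no later. Section 12 names no other origin and makes no allowance for the lead-in.
- **Lead-in.** Section 7.A gives two 28-day ESHAP cycles, with delay possible. Section 7.B: "The rituximab + ibritumomab tiuxetan regimen is given 4-6 weeks after completion of the second cycle of ESHAP".
- **Benchmark.** Section 12.A sets 1-year PFS "compared to what would be expected historically for patients treated with Zevalin without prior cytoreduction", and says that "a 1-year PFS of 67.3% will be considered highly encouraging, compared to an historical rate around 50" percent. It adds: "These values correspond to approximate median times to progression of 21 months and 12 months, respectively, assuming exponential survival". Section 1.E says that TTP and OS "will be compared with reported outcomes in published trials of Zevalin alone".
- **Hypothesis.** Section 1.E expects that cytoreduction "will result in a significant prolongation of time to progression following Zevalin therapy".
- **Objectives.** Sections 2.A.1 and 2.A.2 name 1-year PFS and median TTP in patients given ESHAP followed by Zevalin.
- **Test.** Section 12.C uses a "chi-square test for one binomial population at the one-sided 0.10 significance level", in everyone given at least one ESHAP dose.

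**The concern.** A Zevalin-alone study has no ESHAP phase, so its clock cannot contain an equivalent lead-in. In this trial, twelve months from first ESHAP is only about 9 to 10 months after Zevalin starts. Progression-free weeks on ESHAP therefore count towards the 1-year figure and the median, and both are set beside Zevalin-alone numbers.

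That matters for interpretation. A pass could be read as confirming Section 1.E when time to progression after Zevalin has not changed. The trial is single-arm, so no concurrent control absorbs the offset, and Section 12.C plans no analysis that starts at Zevalin.

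**Working it through.** **1. The plan's own figures.** Inputs (Sections 12.A-12.C): p0 = 0.50, p1 = 0.673, one-sided alpha 0.10, power 0.90, z = 1.2816.

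n = [1.2816·√(0.50·0.50) + 1.2816·√(0.673·0.327)]² / (0.173)² = 51.5, so 52. This matches the plan.

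Critical count = 26 + 1.2816·√13 = 30.62, so the test passes at 31 of 52 (59.6%). Exact binomial: 10.6% at p = 0.50 and 90.6% at p = 0.673. Exponential median at 67.3%: 12·ln 2 / (−ln 0.673) = 21.0 months, as stated.

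**2. Lead-in L (Sections 7.A, 7.B), without delay.** The plan does not say which day completes cycle 2.
- Shortest: Cycle 2 Day 4 is trial day 32; plus 28 days is day 60, so L = 60/30.44 = 1.97 months.
- Longest: Cycle 2 Day 28 is trial day 56; plus 42 days is day 98, so L = 98/30.44 = 3.22 months.

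Twelve months from first ESHAP is then 10.0 or 8.8 months after Zevalin Day 1.

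**3. Chance of passing if nothing changes after Zevalin.** Assumptions: exponential time to progression from Zevalin with a 12-month median; historical clock starting at the Zevalin regimen; a share q progressing before Zevalin (not in the documents; 0-10% shown); everyone else reaches Zevalin.

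p = (1 − q)·0.5^((12 − L)/12), and chance of passing = P(X ≥ 31 | n = 52, p).

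| Lead-in | q | 1-year PFS from ESHAP | Chance of passing |
|---|---|---|---|
| Day 60 | 0% | 56.0% | 35% |
| Day 60 | 5% | 53.2% | 22% |
| Day 60 | 10% | 50.4% | 12% |
| Day 98 | 0% | 60.2% | 59% |
| Day 98 | 5% | 57.2% | 42% |
| Day 98 | 10% | 54.2% | 26% |

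**4. Break-even.** p returns to 0.50, and the chance of passing to 10.6%, when q = 1 − 0.5^(L/12): 10.8% (day 60) or 17.0% (day 98). This is exactly the progression that a 12-month-median hazard produces during the lead-in.

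**5. Median TTP.** With q = 0 the median from first ESHAP is 12 + L = 14.0 or 15.2 months. The lead-in is 1.97/9 = 22% to 3.22/9 = 36% of the 9-month gain sought (12 to 21 months).

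**6. If the primary test were moved to 12 months after Zevalin Day 1**, with failures before Zevalin counted and 31/52 kept, patients would need 12 + L = 14.0 to 15.2 months from ESHAP.
- Sequence equal to Zevalin alone from start of treatment: 0.5^((12 + L)/12) = 44.6% or 41.5%; chance of passing 2.1% or 0.6%.
- Median 21 months from ESHAP: 0.5^((12 + L)/21) = 63.1% or 60.5%; power about 75% or 61%, against 90.6% as planned.

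**The case against.** **The planned clock is legitimate.** The objectives in Section 2.A concern the sequence, and progression-free time on ESHAP is part of what it delivers. Counting both strategies from first treatment is like for like, and keeping every ESHAP-treated patient avoids selecting those who lasted until Zevalin. This stands.

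**A reader might infer that the test is invalid, or that its false-positive rate is really 35-59%.** The documents do not support that. Section 12.A's null is exponential with a 12-month median; applied from first ESHAP, it gives 10.6% (step 4). The higher figures need ESHAP to hold progression below that hazard, which is itself a benefit of the sequence. They are false positives only for the narrower Section 1.E claim. The 59% is also the extreme corner: longest undelayed lead-in and no early progression.

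**A reader might also infer that the primary test should restart at Zevalin.** Step 6 shows that this over-corrects against 50% and loses power at 52 patients.

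**The inputs are uncertain.** The documents do not give the published trials' time zero. Section 1.D.2 quotes Zevalin-alone median TTPs between 10.8 and 12.9 months, or 46-52% at one year if exponential, so the benchmark is approximate. Patients who do not progress but miss Zevalin because of marrow involvement, biodistribution or platelets are not modelled. These limits stand, and so the result is a range.

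None of this supplies an analysis of time to progression after Zevalin. The gap against Section 1.E remains.

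**Conclusion.** The concern holds as a limit on interpretation. The sample size is right for its inputs, and the test answers whether the sequence, counted from start of treatment, beats 50% at one year. It cannot alone support the claim that cytoreduction prolongs time to progression after Zevalin. With that time unchanged, the chance of passing is 12-35% (day 60) or 26-59% (day 98) for q from 10% down to 0%, and the nominal 10.6% at q of about 11% or 17%. These figures rest on exponential survival, a historical clock starting at the Zevalin regimen, and every patient without early progression reaching Zevalin. The true q is unknown. The case is for a cheap addition, not a new primary test.

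**What to change.** 1. **Sections 12.A and 12.C:** keep the all-treated primary test. State that its time zero is first ESHAP and that it judges the sequence.
2. **Section 12.C:** pre-specify a supportive analysis in all ESHAP-treated patients.
   - Estimate the proportion progression-free 12 months after Zevalin Day 1, counting progression or death before Zevalin as failure.
   - Score patients who never start Zevalin at a fixed equivalent date, for example 12 months after trial day 98.
   - Add Kaplan-Meier TTP from Zevalin Day 1. Give confidence limits for both.
3. **Reporting:** show this beside the primary result and say that it is conservative against 50%, because failures before Zevalin count as well. Claim longer time to progression after Zevalin only if it supports that.
4. **Reconcile the schedule:** Section 5.E.1 requires disease assessment every 6 months after Zevalin, but the Appendix A calendar, as extracted, shows none at month 12. Say also where disease status at the fixed date will come from for patients taken off study before 90Y Zevalin (Sections 6.C.5 and 7.B.2).

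Cost: slightly more analysis, a less favourable supportive figure, and a read-out of that figure 2 to 3 months later. The sample size and the primary decision rule do not change.

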3. MEASURABLE LESIONS

• Measurable lesions will be assessed **bidimensionally** at baseline for determining the efficacy of study treatment. Measurable lesions must be measured at baseline by the method which will be used for routine tumor measurement during the study. The patient must have at least one lesion of 2 cm or larger in its longer diameter.

4. DEFINITION OF MEASURABLE DISEASE

b. The extent of disease is measurable if the patient has one or more lesions that are clearly demarcated and may be represented with clearly defined margins as measured in centimeters. These measurements will be bidimensional (two longest perpendicular measures per lesion) meeting the minimum requirement: 1) at least 1.5 cm in a single dimension for all lesions and 2) at least 2.0 cm in a single dimension for at least one lesion. All other lesions will be followed as evaluable disease.

APPENDIX E

- SAE Reporting documents
- MedWatch forms

			SAE Case Reference
	SERIOUS AD	VERSE EVENT	#
biogen idec	FORM	VI (SAE)	
			Biogen Idec use only
Section A:			
Patient	Patient	Site	Protocol
Number:	Initials:	Number:	Number:
DOB:	Patient Gender: □	I Male □ Female Inve	Principal estigator:
Date reported to Biogen			
Idec:	_	Report Type: ☐ Ir	nitial □ Follow-up □ Final
(MM/DD/YY)			
Onset date of event:			
	(MM/DD/YY)		
Section B:	CRITERIA FOR SE	RIOUS CLASSIFICAT	ION
Please check all that apply:			
□ Death		☐ Important medi	cal events (may jeopardize the
(MM/DD/Y	Y)		nd may require medical/surgical
Autopsy performe	ed? □ Yes □ No	intervent	ion to prevent above outcomes)
☐ Life-Threatening			
ŭ		☐ Congenital ano	maly / Birth defect
☐ New / Prolonged Hospital	ization		
	// Discharge Date	☐ Other: specify_	
☐ Persistent / Significant Di	sability / ncapacity		
\$	Section C:	STUE	DY DRUG
Investigational Drug Name:	*	First Treatmer	nt date:
Data of most recent treatment			(MM/DD/YY)
Date of most recent treatme	ent:(MM/DD/	Dose, Frequer	ncy, Route:
Act	ion taken on Study Dru	ug due to Adverse Event:	(check one)
□ None	☐ Dose increased	☐ Dose reduced ☐ Ir	nterrupted
	□ IV rate i	ncreased □ IV rate de	creased

Did Adverse Event abate after stopping drug?

☐ Yes ☐ No ☐ Unknown ☐ N/A

				Form Number: PV 001
Did Adverse Event reappear after reintroduction?	☐ Yes	□No	☐ Unknown	□ N/A
*If Investigational Drug is a combination therapy, specify or	ther suspect com	ponent in	Sections D and	!E

Patient Patient Site Protocol Number: Number: Number: Number: Number: Number: Section D: Section D: SERIOUS ADVERSE EVENT # Biogen Idec use only Biogen Idec use only Number: Numbe			
Patient Patient Site Protocol Number: Number: Number: Number: Number:			
Patient Patient Site Protocol Number: Number: Number: Number: Number:			
Patient Patient Site Protocol Number: Initials: Number: Number:			
Number: Initials: Number: Number:			
Number: Initials: Number: Number:			
Section D: Combination Therapy (Second Component)			
Investigational Drug Name: * First Treatment date:			
(MM/DD/YY)			
Date of most recent treatment: Dose, Frequency, Route:			
(MM/DD/YY)			
Action taken on Study Drug due to Adverse Event: (check one)			
☐ None ☐ Dose increased ☐ Dose reduced ☐ Interrupted ☐ Discontinued			
□ IV rate increased □ IV rate decreased			
Did Adverse Event abate after stopping drug? ☐ Yes ☐ No ☐ Unknown ☐ N/A			
Did Adverse Event reappear after reintroduction? ☐ Yes ☐ No ☐ Unknown ☐ N/A			
Section E: Combination Therapy (Third Component)			
Investigational Drug Name: * First Treatment date: (MM/DD/YY)			
Date of most recent treatment:			
Dose, Frequency, Route:			
Action taken on Study Drug due to Adverse Event: (check one)			
□ None □ Dose increased □ Dose reduced □ Interrupted □ Discontinued			
·			
☐ IV rate increased ☐ IV rate decreased Did Adverse Event abate after stopping drug? ☐ Yes ☐ No ☐ Unknown ☐ N/A			

Did Adverse Event reappear after reintroduction?

☐ Yes ☐ No ☐ Unknown ☐ N/A

Section F: DESCRIPTION OF THE SERIOUS ADVERSE EVENT											
(Include relevant medical history and intercurrent illness)											
Section G: EVALUATION C	NE THE SEE	RIOUS ADVERSE EV	/FI	NT							
Section 6:	i iiil oli		V L I	~ 1							
DELATIONSHIP TO STUDY DRUG		Key	1	OUTCOME AT T	ME OF F	FRORT					
1 = Probably Related	1	GRADE = Mild		OUTCOME AT TIME OF REPORT 1 = Resolved 4 = Worsened							
					5 = Not						
2 = Possibly Related	2	= Moderate		2 = Improved	Available						
3 = Unknown	3	= Severe		3 = Unchanged	d 6 = Fatal						
4 = Not Related **	4	= Life Threatening									
					HS.		ш				
ADVERSE EVENT	B \	ONSET DATE	[DATE STOPPED	ATIONSH	GRADE	OUTCOME				
(list primary diagnosis first, if possible - one p e.g. neutropenic fever	er line)	(MM/DD/YY)		(MM/DD/YY)	RELA ⁻	G. S.	OUT				
					 						
**Specify on "Other Comments" section at	hor factors the	at may have contributed	to ti	he adverse event							

^{**}Specify on "Other Comments" section other factors that may have contributed to the adverse event

1			SAE Case Reference
biogen idec		S ADVERSE EVENT FORM (SAE)	#
			Biogen Idec use only
Patient	Patient	Site	Protocol
Number:	Initials:	Number:	Number:

Section H: TEST PERFORMED TO EVALUATE THE SERIOUS ADVERSE EVENT										
Tests	Date	Result	If Lab, Normal	Clinically S	Significant					
16313	(MM/DD/YY)	Nesuit	Range/Units	YES	NO					

Section I:	TREATMENT A	DMINISTER	RED TO TR	EAT THE	SERIOUS ADVERSE	EVENT
Druc	ر / Therapy	Start Date	Stop Date	Ongoing	Dose / Route	Indication
Diag	у тпогару	(MM/DD/YY)	(MM/DD/YY)	Y / N?	Dose / Noute	malcation

biogen idec	– SERIO	DUS ADVEI FORM (S	ENT	SAE Case Reference # Biogen Idec use on			
Patient	Patient	Si	te		Proto	ocol	
Number:	Initials:	N	lumber:		Num	nber:	
Section J:	(CONCOMIT	ANT THE	RAPY			
	(ongoing or	completed withi	n one week	prior to onset of	event)		
		Not Include					
Drug/Therapy	Start Date	Stop Date	Ongoing	Dose/F	Route	Indication	
Drug/ Micrapy	(MM/DD/YY)	(MM/DD/YY)	Y / N?	D03C/1	toute	indication	
Section K:		OTHER C	OMMEN	TS			
have reviewed the data contai	ned in these page	s and have fo	und it to be	accurate:			
Principal Investigator's Signat	ure			Date Signe	ea		

Title

Name (print)

Institution

Phone Number

Fax Number

For use by user-facilities, Distributors and manufacturers for MANDATORY reporting Page ___ of ___

Form Approved:	OMB No. 0910-0291 Expires 12/31/94
	See OMB statement below
Mfr. report #	
UF/ Dist report #	
	FDA use only

A. Patient Information						pect Medica				
1. Patient identifier 2. Age at	time of event:	3. Sex	4. Weight	lbs.	Name (giv	e labeled strengtl	h & mfr/labele	r, if known)		
Or data		☐ Female	or							
(In Confidence) Or date of birth:		☐ Male		kgs.	#2					
, ,	de et Duckley				2 Doce f	requency & route	used	3 Thorany date	oc (if unl	known, give duration)
B. Adverse Event or Proc	duct Problem				2. Dose, 1	requency & route	useu	from/to (or b		
1. ☐ Adverse event and/or ☐ Pr	roduct problem (e.	g., defects/malf	unctions)		#1			#1		
Outcomes attributed to adverse 6	event				#2			#2		
(check all that apply)	Svene									
	☐ Dis	ahility			4. Diagno	sis for use (indicat	tion)			abated after use ed or dose reduced
☐ Death		ngenital anomal	,		#1					
☐ Life-threatening		quired intervent		nt	" -				1# □Ye	es No Doesn't
		rmanent impairn							2# □∨	apply es □No □Doesn't
☐ Hospitalization – initial or prole	onged 🔲 Otl	ner:			#2				Z# 🗀 II	apply
					6. LOT	# (if known): 7	'. Exp. Da	ate (if	8. Ev	vent reappeared after
3. Date of	3. 0	ate of			0. 201	# (II KIIOWII). /	known):	ite (ii		roduction:
event	t	his report			#1:		#1:		1 # 🗖 V	es No Doesn't
(mo/day/yr) to	(mo/day/yr)					#1:		1# 🔲 16	apply
					#2:		#2:			
4. Describe event or problem:		_			9. NDC	# - for product p	roblems only (if known)	2# □Y	es No Doesn't
Please see page two for additional	i information of thi	s event.								apply
					10. Concor	mitant medical pro	oducts and the	rapy dates (exc	lude tre	atment of event)
								.,		··· · · · · · · · · · · · · · · · · ·
					D All	Manufactu	rers			
						office – name/ad		g site for device	es):	2. Phone number:
										3. Report Source: (check all that apply)
										Foreign
										☐ Study
_				_	L			5 ND4 "	_	Literature
r icase see page unice for laborate	,, , , , , , , , , , , , , , , , , , ,				4. Date	received by manu	ufacturer	5. NDA # IND #		Consumer
								PLA #		☐ Health professional
					6. If, IND,	protocol #				☐ User facility
								Pre-1938	Yes	☐ Company
					7. Type of				Yes	representative
					(спеск ап	I that apply)		product		☐ Distributor ☐ Other:
					☐ 7-day	☐ 15-da	ау			□ Other.
					☐ 10-day	☐ perio	dic	8 Adverse ev	ent term	n/e)
					☐ Initial	☐ follow	v-up #			
6. Other relevant history, includin					9. Mfr.	report number				
pregnancy, smoking and alcohol ι	use, nepatic/renai	aysrunction, etc.	.):							
						ial Reporte				
					1. Name,	address & phone	#			
— A					2 Health	professional?	3. Occupa	tion	4	Initial reporter also
	on of a report do on that medical pe						J. Occupa	uon		sent report to FDA?
FDA Form 3500A (6-93) Distributo	r, manufacturer				☐ Yes	□ No			[□Yes □No □Unk
	ed to the event. t or sponsor, and a					:¢	s it displays a	nurrontly valid (MP sam	tual mumbau"

For use by user-facilities, Distributors and manufacturers for MANDATORY reporting Page ____ of ____

Form Approved: OMB No. 0910-0291 Expires 12/31/94
See OMB statement below
Mfr. report #
UF/ Dist report #
FDA use only

For use by user-facilities, Distributors and manufacturers for MANDATORY reporting Page ____ of ____

Form Approved:	OMB No. 0910-0291 Expires 12/31/94
	See OMB statement below
Mfr. report #	
UF/ Dist report #	
	FDA use only

FDA Form 3500A (6-93)

Submission of a report does not constitute an admission that medical personnel, user facility, distributor, manufacturer or product caused or contributed to the event.

"An agency may not conduct or sponsor, and a person is not required to respond to, a collection of information unless it displays a currently valid OMB control number"

